4.2 Analysis sets

Subjects will be screened to determine if they meet all inclusion and no exclusion criteria. Subjects will be analyzed according to the treatment they actually received. The following analysis sets will be used in the study:

- **Safety Analysis Set:** Includes all subjects who received any (even a partial dose) investigational product (KHK4083 or placebo); The Safety Analysis Set will be used to perform all safety analyses as the basis for all summaries proposed in this SAP.
- **Full Analysis Set (FAS):** Includes all subjects who receive at least one full dose of investigational product and who have Baseline data and at least one post-treatment assessment of the primary efficacy variable. Summaries of efficacy will be presented for the FAS.

	Forms			
	Title	Statistical Analysis Plan Template		
	Code	Version	Effective Date	Page
	FRM_ST03_032	01	23 Apr 2015	23 of 53

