6.1.1 Induction Therapy: Week 0 to Week 12 (Last Dose at Week 10)

Double-blind Induction Therapy is separated into Part A for administration of multiple ascending IV doses of KHK4083 (or placebo) to subjects in Cohorts 1 - 3 and Part B for administration of the recommended IV dose (one of three dose levels identified in Part A) of KHK4083 (or placebo) to subjects in Cohort 4. Subjects in Part A are prohibited from participating in Part B.

Subjects in each cohort will be randomly assigned in a 3:1 ratio to receive KHK4083 or placebo by IV infusion over 60 minutes (\pm 10 minutes). Each subject will receive a total of 6 treatments (one IV infusion per treatment) every 2 weeks from Week 0 (Day 1) to Week 10 of Induction Therapy. Safety assessments (e.g., after 2 treatments for 1.0 mg/kg and 3 treatments for 3.0 and 10 mg/kg are administered and 14-day safety data from the last treatment are available) will determine whether dosing will continue for subjects within a cohort and if the investigational product will be administered at the next higher dose level for subjects in the next cohort in Part A or for Cohort 4 in Part B (refer to Section 6.3 for details on the Safety Monitoring Plan).

For subjects in all cohorts, a sigmoidoscopy with biopsy is scheduled at Week 12 to assess improvement in the mucosa from Baseline (Week 0) to Week 12. It is highly recommended that the sigmoidoscopy with biopsy be performed within 7 to 13 days prior to the Week 12 visit. The sigmoidoscopy results from the central reader are required before a subject receives treatment in the OLE/LTE Therapy phase.

6.1.2 Long-term Extension Therapy: Week 12 (First Dose) to Week 52

The LTE is only active for subjects who entered it prior to approval of Amendment 2. Subjects who sign an ICF under Amendment 2 are eligible for the OLE (see Section 6.1.3).

Subjects who completed double-blind Induction Therapy (i.e., at least five of six treatments) and had a clinical response or mucosal healing were eligible to continue in double-blind LTE Therapy. A clinical response is defined as a reduction in the total Mayo Clinic score of at least 3 points and a decrease of at least 30% from Baseline (Week 0) to Week 12, and a reduction in the rectal bleeding subscale of at least 1 point from Baseline (Week 0) to Week 12 or an absolute rectal bleeding score of 0 or 1 at Week 12. Mucosal healing is defined as a mMES of 0 or 1.

All subjects who qualified were to have been given two options:

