4.1 General

General descriptive statistics for continuous variables include the n (number of observed values), the mean, standard deviation, median, minimum, and maximum values. For categorical variables, the number and percentage of subjects with a specific level of the variable will be presented. The percentage will be calculated using the subjects with a reported value. Counts of missing subjects will be identified for variables that had one or more subjects with a missing result. Descriptive statistics will be presented by treatment Cohort (KHK4083 dose levels; combined KHK4083; and placebo) and by visit.

Unless there are any notes, the following rules will be applied for all tables and figures;

- Data from placebo subjects in each Cohort will be combined, not depending on treatment period (Double-Blind Induction Therapy, Long-Term Extension Therapy, Open-Label Extension Therapy, or Follow-up).
- In the case that Screening or Baseline is necessary in the tables and figures related to LTE Therapy Period, OLE Therapy Period, or Follow-up Period, the data at Screening or Baseline will be used or displayed.
- Double-Blind Therapy Period will be defined as the period including both Double-Blind Induction Therapy Period and LTE Therapy Period.
- When “Week xx” (xx: number) is necessary, “Week xx” displayed on CRF will be used or displayed.

To explain how data are summarized, the figure showing the relationship between period and dose of Investigational Product is displayed in Figure 3 and the table defining the category is displayed in Table 2.

[figure not shown]
	Forms			
	Title	Statistical Analysis Plan Template		
	Code	Version	Effective Date	Page
	FRM_ST03_032	01	23 Apr 2015	20 of 53

Figure 3 Relationship between Period and Dose of Investigational Product

Subjects who do not move to OLE/LTE Therapy

Subjects who move to OLE/LTE Therapy

[figure not shown]

Table 2 Category in Tables and Figures

	4083 Randomized				Placebo Randomized			
	Cohort 1	Cohort 2	Cohort 3	Cohort 4	Cohort 1	Cohort 2	Cohort 3	Cohort 4
Summary Pattern	Category In Tables and Figures							
Double-Blind Induction Therapy Period	1.0 mg/kg	3.0 mg/kg	10 mg/kg	1.0, 3.0 or 10 mg/kg	Placebo			
Double-Blind Therapy Period ¹⁾								
Double-Blind Therapy Period and Double-Blind Therapy Follow-up Period ²⁾								
LTE Therapy Period								
LTE Therapy Period and Double-Blind Therapy Follow-up Period	1.0 mg/kg	3.0 mg/kg	10 mg/kg	1.0, 3.0 or 10 mg/kg	Placebo ³⁾			

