7.1 Analysis of primary endpoint

The primary efficacy endpoint is the mean change in mucosal score presented by mMES (subscores from 0 to 3 with modified endoscopy finding scoring, i.e., excluding mild friability from a subscore of 1) from Baseline (Week 0) to Week 12 for all subjects who received the recommended dose during Induction Therapy. This includes Part A subjects who received the recommended dose identified for Part B as well as the subjects who received the recommended dose during Part B of Induction Therapy. Change from Baseline in mMES as well as Baseline and Week 12 will be summarized by treatments (each KHK4083 dose level and placebo) by means of descriptive statistics (number of subject n, mean, standard deviation, median, min and max); the 95% confidence Interval (CI) for the change from baseline will be derived as follow:

$$\text{Upper 95\%CI} = \mu_x + t(\alpha, df)SE(\mu_x)$$

$$\text{Lower 95\%CI} = \mu_x - t(\alpha, df)SE(\mu_x)$$

where:

- μ_x is the arithmetic mean estimate of the change from baseline
- t is the value from a t table distribution with $\alpha = 0.05$ and df degree of freedom

SE is the Standard error of the mean estimate.

A comparison between treatments (each KHK4083 dose level versus placebo) will be performed using an ANCOVA model with change from Baseline in mMES as dependent variable and treatment as fixed effect and baseline value as covariate. The number of subjects and the number of subjects considered in the model will be provided by treatment. The adjusted means for treatments (least squares means) and the relative 95% CIs will be presented. The difference between the adjusted means for each treatment groups from placebo (Difference in Least Squares Mean from Placebo) will be calculated with the relative 95% CI and p-value. Least squares means with 95% CIs and differences in least squares mean from placebo with 95% CIs will be graphically presented.

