9.2 Programming conventions

All tables/listings will be presented in landscape format.

The standard font size is 9 points Courier New for all tables. Listings will be presented with an 8 or 7 points Courier New.

Titles will be center-aligned; footnotes will be left-aligned.

Each table/figure/listing will have 2 titles:

- The 1st title will be the table/figure/listing number with the description of the table/figure /listing;
- The 2nd title will be a description of the study population presented in the table/figure/listing. Some tables will have another title (before 2nd title) with a description of the statistical method used in those tables.

Any footnote added to explain the table/listing/figure contents will be presented in the following format:

Note 1: Percentages are calculated on the number of subjects (N).

Note 2: A serious adverse event is an....

Note 3:

The last two footnotes of each table/figure will be footers indicating:

- the reference listing of the data;
- the program name, the date and time of generation and the SAS[®] version used.

The last footnote of each listing will be a footer indicating the program name, the date and time of generation and the SAS[®] version used.

	Forms			
	Title	Statistical Analysis Plan Template		
	Code	Version	Effective Date	Page
	FRM_ST03_032	01	23 Apr 2015	38 of 53

In the tables and listing the treatment under comparison will be labeled as “Cohort 1 1.0 mg/kg”, ‘Cohort 2 3.0 mg/kg’ “Cohort 3 10 mg/kg”, ‘Cohort 4 XX mg/kg’ (XX is the recommended dose) and “Placebo”.

In tables and figures, unless otherwise stated, the number of subjects corresponding to analysis set will be shown at the part of “N=XX” together with the labels of treatment group.

- For example, in Table 14.3.1-1.1 “Overall summary of treatment-emergent adverse events during study / safety analysis set”, the part of “N=XX” will display the number of subjects in safety analysis set corresponding to the labels of the treatment group (e.g. 1.0 mg/kg, 3.0 mg/kg, 10 mg/kg, Placebo) and All.

Unless otherwise stated, listings will be presented by randomized treatment, and sorted by cohort and the site-subject identifier.

Except for the listings 16.2.1-1.2 (based on screening failure subjects) and 16.2.1-1 (based on all subjects), all the listings will be based on the randomized subjects.

In all the listings on safety variables, a column with a flag (§) for treatment misallocation will identify the treatment misallocations.

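### SAP 4.2 applies analysis by treatment received to the efficacy set as well as the safety set, which conflicts with the randomised categories in Table 2 and the by-randomised listings in SAP 9.2

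*SAP*

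**What the plan says.** SAP 4.2 opens with a general rule, "Subjects will be analyzed according to the treatment they actually received", and then defines the Safety Analysis Set and the FAS. No exception is made for the FAS. Its membership rule, where the assessment meant is the mMES, reads: "Includes all subjects who receive at least one full dose of investigational product and who have Baseline data and at least one post-treatment assessment". The same section adds: "Summaries of efficacy will be presented for the FAS".

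SAP 7.1 also words the primary population by receipt. The sentence, which closes with a reference to the second part of Induction, begins: "This includes Part A subjects who received the recommended dose identified for Part B as well as the subjects who received the recommended dose during". The analysis is then set out: "A comparison between treatments (each KHK4083 dose level versus placebo) will be performed using an ANCOVA model with change from Baseline in mMES".

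Other parts of the SAP use randomised assignment. Table 2 in SAP 4.1 defines the categories for tables and figures under "4083 Randomized" and a matching heading for placebo. Its footnote 3 keeps placebo-randomised subjects in one placebo category while they receive KHK4083. SAP 9.2 presents listings by randomised treatment unless otherwise stated and adds, for listings of safety variables, that "a column with a flag (§) for treatment misallocation will identify the treatment misallocations".

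The Protocol specifies randomisation within cohort: "Subjects in each cohort will be randomly assigned in a 3:1 ratio to receive KHK4083 or placebo by IV infusion". Sections 12.2 and 12.3 do not say whether the FAS is analysed as randomised or as received, so they do not settle the matter.

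**The concern.** Grouping by treatment received is a usual choice for safety. For efficacy it means that arm membership can be changed by something that happens after randomisation. SAP 4.2 does not separate the two uses, and no as-randomised efficacy analysis is planned alongside.

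The SAP also gives no single answer. A programmer following 4.2 and one following Table 2 could put the same misallocated subject in different columns of the primary table. If the choice is left to programming, it may be made after treatment codes are known. The Week 12 results feed the proof-of-concept decision described in SAP 4.5, so the rule should be fixed beforehand.

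SAP 4.2 also does not say what treatment received means for a subject given the wrong product at only some of the six Induction infusions.

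**Working it through.** **1. The plan's own counts.** SAP 3.2 and Protocol 12.3.4 plan 60 randomised to give 51 evaluable with 15% dropout: 51 / (1 − 0.15) = 60, which reproduces. Arms: 9 + 18 = 27 at the recommended dose; 3 × 3 + 6 = 15 on placebo. Evaluable at 15% dropout: 15 × 0.85 = 12.75 placebo (about 13) and 27 × 0.85 = 22.95 (about 23). There is no power calculation to reproduce, and the choice of rule does not change the planned N.

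**2. One subject, several rules.** Suppose a subject randomised to placebo in Cohort 2 is given KHK4083 3.0 mg/kg throughout Induction.

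- SAP 4.2: analysed as 3.0 mg/kg.
- SAP 4.1, Table 2: placebo.
- SAP 9.2: listed under placebo, with a misallocation flag in the safety listings only.
- SAP 7.1: counted with the recommended dose if that dose is 3.0 mg/kg, because the population is worded by receipt.

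**3. Weight of one subject.** Placebo: 1/15 = 6.7% planned, 1/12.75 = 7.8% evaluable. Recommended dose: 1/27 = 3.7%. A non-recommended dose: 1/9 = 11%.

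**4. Shift in the placebo mean.** If the subject's mMES change differs by d from the mean of the other placebo subjects, including or excluding that subject moves the placebo mean by d/n, where n counts the subject. With d = 1.5 (assumed): 1.5/15 = 0.10 and 1.5/12.75 = 0.12. If the subject instead joins an arm of 15, the shift is 1.5/16 = 0.09.

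**5. Shift in the treatment difference (unadjusted means).** Moving a subject alters both arms. Let y be the subject's change, m_K and m_P the means of the other subjects in each arm, n_P the placebo count with the subject and n_K the active count without. Moving from placebo to KHK4083 shifts the difference by

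(y − m_K)/(n_K + 1) + (y − m_P)/n_P.

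With a baseline mMES of 2 or 3 (Protocol 7.2, criterion 5b), y can run from −3 to +1. The documents give no arm means, so m_P = −0.5 and m_K = −0.5 or −1.0 are assumed.

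- 27 versus 15, y = −3, both means −0.5: −2.5/28 − 2.5/15 = −0.089 − 0.167 = −0.256.
- 27 versus 15, y = −1, m_K = −1.0: 0/28 − 0.5/15 = −0.033.
- Over all cases, and in both directions of misallocation, the absolute shift is about 0.03 to 0.26 points. With 23 versus 13 it is about 0.04 to 0.30.
- With d = 1.5 from both means: 1.5/28 + 1.5/15 = 0.054 + 0.100 = 0.154.

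With no misallocation every shift is 0.

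**The case against.** The strongest reply is that Table 2 may already govern the outputs. If so, the primary table is by randomised arm and the sentence in 4.2 is loose drafting. This has weight: the SAP cannot be said to group every output by receipt. But the two rules still conflict, and 4.2, which defines the analysis sets, is the more explicit of the two.

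A second reply is that the risk is small and the trial exploratory. An unblinded pharmacist prepares each dose from the IRT assignment (Protocol 8.3), no misallocation rate is given, Protocol 12.3.5 calls all analyses descriptive or exploratory, and SAP 4.1 disclaims hypothesis testing. All of this stands and limits the size of the point.

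Stronger readings are tempting but not supported:

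- A reader might infer that the as-received rule removes the basis for the confidence intervals and p-values in SAP 7.1 and 7.2. It does not. With no misallocation the two rules give identical arms.
- A reader might infer that this sentence alone separates the analysis from a strictly randomised one. Placebo is already pooled over sequential cohorts with no cohort term in the model, and FAS entry requires a full dose and a post-treatment score. Changing the sentence leaves those features in place.
- A reader might cite cohort-level dose reduction as a further case. Under Protocol 8.1.3.4 it applies to all subjects in a cohort, so the dose label is equally unclear under either rule.
- A reader might take the flag in SAP 9.2 as a forecast of misallocation. It only provides for the possibility.

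**Conclusion.** The point holds in a limited form. As written, SAP 4.2 extends analysis by treatment received to the efficacy set and disagrees with Table 2 and the listings convention. The consequence depends entirely on a subject receiving the wrong treatment during Induction; otherwise nothing changes.

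If one subject is affected, about 7 to 8% of the placebo arm moves, and the placebo mean shifts by roughly 0.1 mMES points for an assumed 1.5-point deviation. Under the assumed arm means, the unadjusted difference could move by up to about 0.26 points (0.30 at the evaluable counts), but only for a subject with the extreme change of −3. These are illustrations on unadjusted means. The ANCOVA adjusts for baseline, and the documents supply neither arm means nor a misallocation rate.

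The change is worth making because it is a stated rule with a specific correction at almost no cost, and the Week 12 result informs a development decision.

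**What to change.** In SAP 4.2, replace the single sentence with a rule for each set:

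- The FAS is analysed by randomised treatment (the cohort's KHK4083 dose, or placebo).
- The Safety Analysis Set is analysed by the treatment actually received in the Double-Blind Induction and LTE periods, with a stated rule for which column takes a subject who received more than one treatment or dose in a period.

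Keep Table 2 footnote 3, so that placebo-randomised subjects in the OLE remain a separate category. A blanket rule counting anyone who received KHK4083 as KHK4083 would contradict that footnote and force the OLE safety tables to be regrouped.

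Add a note to Table 2 that its randomised headings apply to efficacy, and that safety outputs for Induction and LTE follow the second rule. Make SAP 9.2 consistent, and read the receipt wording in SAP 7.1 as assignment to the recommended dose. Optionally, add an as-received efficacy sensitivity analysis, to be run only if misallocation occurs.

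The cost is a short SAP edit and a check of the treatment variable used in the Week 12 programs. It needs no new data and no change in sample size. It is best settled before the unblinding described in SAP 4.5, so that the choice cannot appear to depend on results.

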7.5.3 Criteria for Subject Removal from Treatment and the Study

In the absence of a medical contraindication or significant protocol violation, every effort will be made by the Investigator to keep the subject in the study. However, if the Investigator concludes that it is in the best interest of the subject to discontinue administration of the investigational product, including subjects who have not benefited from treatment or should

the subject decide to discontinue study treatment, all efforts will be made to complete and report the observations as thoroughly as possible.

Investigational product administration will be stopped if any of the following events occur:

- Subject experiences a second SUSAR of the same SOC;
- Subject experiences a severe AE that is related to the investigational product;
Investigational product administration may be withheld for up to 2 weeks if the subject experiences a severe event in which it is unclear if the event is related to the investigational product. This will allow the Investigator to determine if the event is related to the investigational product prior to removing the subject permanently from the study.
- Subject experiences a severe, acute infusion reaction despite administration of a prophylactic pre-medication regimen or if the subject experiences anaphylaxis regardless of having received a pre-medication regimen or not. Anaphylaxis has symptomatic bronchospasm and/or allergy-related edema/angioedema as the principal clinical manifestation(s); refer to the clinical diagnostic criteria of anaphylaxis defined in Appendix 5);
- Subject has two consecutive visits during Induction Therapy with a worsening from Baseline in partial Mayo Clinic score of ≥ 3 points (e.g., partial Mayo Clinic score of 3 at baseline, 6 at Week 2, and 6 at Week 4) or two consecutive visits during maintenance therapy with a worsening from Week 12 in partial Mayo Clinic score of ≥ 3 points at a visit and ≥ 5 points at the next visit unless the Investigator, with agreement from the Sponsor, determines that there has not been clinically significant worsening, in which case the subject may continue to receive study medication at that visit (agreement from the Sponsor is to be obtained for each visit);
- Surgery and/or use of prohibited medications are needed to treat the worsening of UC;
- Subject requires a concomitant medication that is prohibited in the study;

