7.5.4 End-of-Treatment Visit

An End-of-Treatment visit must be conducted for all subjects who discontinue from treatment. This visit must occur within 2 weeks or 4 weeks after the last dose of investigational product of Induction Therapy or OLE/LTE Therapy, respectively.

If the subject discontinues during Induction Therapy, the assessments listed in Table 9.1 for End-of-Treatment/Week 12 should be performed at the End-of-Treatment visit. A sigmoidoscopy will be performed at End-of-Treatment/Week 12 if the subject discontinues more than 8 weeks after Baseline visit; the sigmoidoscopy may be performed up to 4 weeks after the last dose of study medication. Post-treatment follow-up visits should subsequently occur 4, 8 and 14 weeks after the End-of-Treatment/Week 12 visit.

If the subject discontinues during OLE/LTE therapy, the assessments listed in Table 9.2 for End-of-Treatment/Week 52 should be performed at the End-of-Treatment visit. A sigmoidoscopy will be performed at End-of-Treatment/Week 52 if the subject discontinues more than 8 weeks after the Week 12 visit; the sigmoidoscopy may be performed up to 8 weeks after the last dose of study medication. Post-treatment follow-up visits should subsequently occur 4, 8 and 12 weeks after the End-of-Treatment/Week 52 visit.

The Investigator must complete all applicable End-of-Treatment visit procedures (e.g., sigmoidoscopy, safety laboratory parameters, ECG, physical examination, vital signs) and applicable eCRF pages for subjects who discontinue treatment and include the reason for discontinuation of treatment.

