- g: Female subjects considered to be women of childbearing potential must have a negative pregnancy test at Screening and Baseline. Subjects are considered to not be of childbearing potential if they are ≥ 50 years of age and without menses for 24 consecutive months; have an FSH level > 25 mIU/mL (or in postmenopausal range per local laboratory standards); or have undergone a hysterectomy and/or a bilateral salpingo-oophorectomy.
- h: Subjects with a low risk of an infection only need an interferon gamma release assay.
- i: For the delayed-type hypersensitivity test, the skin testing site will be read within 48 to 72 hours following intradermal injection of the *Candida albicans* antigen. The largest diameter of induration will be measured in mm and collected.
- j: If the subject discontinues more than 8 weeks after the Baseline visit, a sigmoidoscopy must be performed at End-of-Treatment. The sigmoidoscopy may be performed up to 4 weeks after the last dose of study medication.
- k: Fecal calprotectin concentration, which is usually elevated in subjects with moderately active UC, will be measured. Fecal samples will be collected as specified in the stool collection instruction section of the laboratory manual.
- l: Samples for anti-KHK4083 antibodies must be taken prior to dosing and taken at the same time as pre-dose PK samples shown in Table 10.4.1-1 and Table 10.4.1-2.
- m: Whole blood will be collected and stored (frozen) for potential exploratory biomarker analyses in the future at: Baseline (Week 0), Week 2, Week 12 (End-of-Induction Therapy), and Induction Therapy Post-treatment Follow-up 3 visit (if the subject does not continue in OLE Therapy).
- n: The collection of adverse event information should commence following the subject’s written consent to participate in the study.

Footnotes to Table 9-1.(cont'd)

o: All medications (including prescription, non-prescription and supplements) for treatment of UC taken within 6 months prior to Screening; any other medication taken 1 month prior to Screening; and any concomitant medications (including tracking probiotic usage) during the study must be recorded. For all biologic treatments, the reason for discontinuation should be recorded at Screening.

p: All subjects are required to remain at the investigative site to be carefully monitored after each infusion for potential infusion reactions or other adverse events. Post-infusion safety monitoring is as follows:

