12.3.4 Sample Size Determination

Assuming a 15% dropout rate, it is anticipated that approximately 60 subjects will be required to be randomized in order to achieve 51 evaluable subjects in the FAS. In Part A (Cohorts 1 - 3), the sample size is based on the feasibility of the safety and tolerability assessment to recommend starting the treatment of the next cohort of 12 subjects/cohort (9 subjects to receive KHK4083 and 3 subjects to receive placebo). In Part B (Cohort 4) for the treatment of 24 subjects (18 subjects to receive KHK4083 at the recommended dose based on the safety and tolerability in Part A and 6 subjects to receive placebo), the sample size is based on the feasibility of exploratory assessments in efficacy and safety at the recommended dose level. Based on the UCEIS and Mayo Clinic scores and from combining Part A and Part B, it is planned to have approximately a total of 27 randomized subjects receive the recommended dose of KHK4083 and 15 subjects receive placebo.

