12.6 Procedures for Missing, Unused, and Spurious Data

Missing values will not be substituted by estimated values, but treated as missing in the statistical evaluation. All data from all subjects dosed in the study will be included in all listings, plots, summary tables, and statistical analyses when appropriate.

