Appendix 6 Follow-up and End-of-Study for Subjects who Discontinued During the Study

DC=discontinuation; EOT=end-of-treatment; FU=follow-up; LTE=long-term extension; OLE=open-label-extension; w=week

a: EOT visit within 2 weeks after the last dose of IP. Endoscopy will be performed if the subject discontinues more than 8 weeks after Baseline visit.

b: EOT visit within 4 weeks after the last dose of IP. Endoscopy will be performed if the subject discontinues more than 8 weeks after Week 12 visit.

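### Subjects who stop at or before 8 weeks of induction have no planned route into the FAS, so the Week 12 responder rates and partial Mayo analyses leave them out

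*SAP*

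**What the plan says.** **Entry to the FAS.** Protocol 12.2 and SAP 4.2 require at least one full dose and, in the SAP's words, cover subjects "who have Baseline data and at least one post-treatment assessment of the primary efficacy variable. Summaries of efficacy will be presented for the FAS". Protocol 10.1.1 and SAP 3.4.1 make the primary variable the change in mMES. Protocol 12.3 and SAP 7 put efficacy in the FAS.

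**Endoscopy after stopping.** Three places agree:
- Protocol 7.5.4: "A sigmoidoscopy will be performed at End-of-Treatment/Week 12 if the subject discontinues more than 8 weeks after Baseline visit".
- Table 9-1, footnote j: "If the subject discontinues more than 8 weeks after the Baseline visit, a sigmoidoscopy must be performed at End-of-Treatment".
- Appendix 6: "Endoscopy will be performed if the subject discontinues more than 8 weeks after Baseline visit".

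Table 9-1 schedules no sigmoidoscopy at Weeks 2 to 10 or at the follow-up visits. It does schedule a partial Mayo score at all of them.

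**Stopping for worsening.** Protocol 7.5.3 stops treatment when the partial Mayo score is at least 3 points worse than Baseline at two consecutive induction visits. Its example is "partial Mayo Clinic score of 3 at baseline, 6 at Week 2, and 6 at Week 4". The same bullet lets treatment continue if the Investigator judges, and the Sponsor agrees, that the worsening is not clinically significant.

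**Missing data and denominators.** Protocol 12.6: "Missing values will not be substituted by estimated values, but treated as missing in the statistical evaluation". SAP 4.1: "The percentage will be calculated using the subjects with a reported value". SAP 4.4 instead bases percentages on the number of subjects in the treatment or cohort group.

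**Expected loss.** Protocol 12.3.4, assuming 15% dropout: "it is anticipated that approximately 60 subjects will be required to be randomized in order to achieve 51 evaluable subjects in the FAS".

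**The concern.** An endoscopy condition decides who counts in outcomes that are not all endoscopic, and it screens out subjects by how early they stopped. Early stopping in induction is unlikely to be unrelated to outcome. Protocol 7.5.3 lists confirmed worsening, a related severe adverse event and the need for prohibited medication among the reasons to stop, and the worsening rule can act from Week 4.

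The five Week 12 responder rates are affected: mMES improvement, modified Baron improvement, mucosal healing, clinical response and clinical remission. If the subjects left out are non-responders, each stated rate is too high. If the losses differ by arm, the difference from placebo changes as well.

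The partial Mayo loss has no data-based reason. A subject who worsens at Weeks 2 and 4 and then stops has scores showing it. Those scores leave the induction table (14.2-2.3) and the MMRM (14.2-3.8.4), both labelled FAS, and remain only in Listing 16.2.6-2.2.

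The responder table (14.2.2.4) is in the unblinded Week 12 package in SAP 9.4.1. SAP 4.5 uses those results for the proof-of-concept determination.

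**Working it through.** **1. Reproduce the plan's figure** (Protocol 12.3.4). 51 / (1 − 0.15) = 60, and 60 × 0.85 = 51. The cohort counts agree: 3 × 12 + 24 = 60 in total, 9 + 18 = 27 at the recommended dose, 9 + 6 = 15 on placebo. The plan therefore expects 60 − 51 = 9 subjects outside the FAS.

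**2. Is there another way in for an early stopper?**
- Protocol 12.7 includes all dosed subjects unless otherwise specified. For efficacy, the FAS is specified.
- SAP 4.4 uses the number in the group, but SAP 9.2 sets the N shown in tables to the analysis-set N, which here is the FAS.
- Under SAP 4.1 they would be omitted anyway, having no reported Week 12 value.
- An unscheduled endoscopy might satisfy the FAS wording, but SAP 4.1 keeps unscheduled post-dose data out of the summary tables.
- No non-responder rule and no second efficacy set is given.

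None of these brings them back.

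**3. Effect on a rate.** With r responders, N dosed and d early non-responders, the all-dosed rate is r/N and the FAS rate is r/(N − d). Their ratio is N/(N − d). With N = 60:

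| d (assumed) | Ratio |
|---|---|
| 0 | 60/60 = 1.00 |
| 3 | 60/57 = 1.05 |
| 6 | 60/54 = 1.11 |
| 9 | 60/51 = 1.18 |

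The last row is a ceiling. It needs all nine expected losses to be dosed, to stop at or before 8 weeks and to be non-responders. It applies to the trial as a whole, or to each arm if losses are proportional. An arm that takes more than its share can exceed it.

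**4. Effect on the difference from placebo.** Responder counts and losses by arm are assumptions, since the documents give none. Fifteen percent of 27 + 15 = 42 is about 6 losses, or about 4 and 2 if proportional. All losses are taken as non-responders.

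| Assumed responders | Lost (active, placebo) | Difference, points |
|---|---|---|
| 10 active, 3 placebo | none | 10/27 − 3/15 = 17.0 |
| | 2, 1 | 10/25 − 3/14 = 18.6 |
| | 4, 2 | 10/23 − 3/13 = 20.4 |
| | 5, 1 | 10/22 − 3/14 = 24.0 |
| | 3, 3 | 10/24 − 3/12 = 16.7 |
| 8 active, 4 placebo | none | 8/27 − 4/15 = 3.0 |
| | 4, 2 | 8/23 − 4/13 = 4.0 |
| | 2, 4 | 8/25 − 4/11 = −4.4 |

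The shift can go in either direction.

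**5. Against sampling error.** For 10/27 v 3/15, the 95% half-width is 1.96 × √(0.370 × 0.630/27 + 0.2 × 0.8/15) = 0.272, about 27 points. The largest shifts above are about 7 points.

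**6. Visit labels.** Protocol 7.5.4 has an early stopper complete the End-of-Treatment/Week 12 assessments within 2 weeks of the last dose, and Table 9-1 gives these one column. SAP 4.1 analyses by nominal time point without reclassifying, while SAP 5.1 treats Week 12 and End of treatment as separate CRF pages. So the plan does not settle whether a valid endoscopy after 8 weeks counts as Week 12. Nor does it settle whether a partial Mayo score taken near Week 4 or 6 could be read as Week 12.

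**The case against.** **Low stakes.** Protocol 12.3.5 calls all analyses descriptive or exploratory, and SAP 4.1 plans no hypothesis testing. The rates are secondary, and no proof-of-concept criterion based on them is given. This stands and limits the severity. A reader might infer that the primary result is compromised. It is not changed by this rule: the mMES ANCOVA needs an observed change, so without imputation it omits these subjects in any analysis set.

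**The 8-week limit is deliberate.** The amendment's rationale says a shorter time on treatment is too short for an end-of-treatment sigmoidoscopy. That stands as a reason not to look. It is not a reason to remove the subject from clinical outcomes already recorded.

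**The worsening rule has an exception.** This also stands. The protocol's Week 2 and Week 4 example illustrates the score threshold. A reader might infer that such a subject must stop at Week 4, but the same bullet allows treatment to continue.

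**Counting early stoppers as non-responders is a choice of estimand**, above all for those who stop for an adverse event. That is fair, and it is why the FAS rates should be kept alongside.

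**The rates can be rebuilt.** Set counts, listed reasons for exclusion (SAP 5.1) and listings of randomised subjects largely allow it. No summary table shows them, however, and SAP 9.4.1 lists tables only.

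**The MMRM is exploratory and outside the Week 12 package.** Correct. The proof-of-concept argument covers the responder table and the Week 12 partial Mayo tables, not the MMRM.

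**Conclusion.** The point holds at minor to moderate severity. Followed as written, the plan gives subjects who stop at or before 8 weeks no planned route into the FAS. That can inflate the Week 12 responder rates, and it discards usable partial Mayo scores.

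The factor lies between 1.00 and 1.18 for the trial as a whole, if early stoppers are non-responders and losses match the planned 15%. Three stronger readings are not supported:
- **That 1.18 is the expected inflation.** The documents do not say how many of the nine losses are dosed, or when they stop.
- **That the bias favours KHK4083.** The direction depends on losses by arm, which are unknown.
- **That the proof-of-concept decision would change.** No criterion is stated, and the illustrated shifts are well inside sampling error.

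The reason to act is that the responder table feeds that determination, the data are already collected, and a rule fixed before unblinding is more credible than one chosen afterwards.

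**What to change.** Before the Week 12 unblinding, amend the SAP:

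1. Report the Week 12 binary endpoints in all dosed subjects, by treatment received, counting missing Week 12 status as non-response. Keep the FAS rates as a sensitivity analysis.
2. For efficacy percentages, let the SAP 4.4 denominator govern over SAP 4.1.
3. Run the partial Mayo tables and the MMRM in dosed subjects with a Baseline and at least one post-dose partial Mayo score.
4. Add a visit-mapping rule. An End-of-Treatment endoscopy done after more than 8 weeks is analysed as Week 12. An earlier End-of-Treatment partial Mayo score goes to the scheduled visit nearest its actual date, not to Week 12. Without this, step 3 could bring in a new bias.
5. Record these as departures from Protocol 12.2 and 12.3 (FAS for efficacy) and 12.6 (missing data), reported under 12.8.

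The mMES ANCOVA stays as planned apart from the endoscopy visit label in step 4. No new data or procedures are needed. The cost is SAP text, some reprogramming of the responder and partial Mayo outputs, and somewhat lower stated response rates.
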